# Evidence from our previous research

The proposed complex intervention, with the seven facets outlined above, builds on the foundation of previous research conducted by members of the research team. JS conducted an NHS-funded public engagement and multi-agency study on domestic abuse and child safeguarding, in which ten focus groups

were conducted with multi-agencies and the public. The most striking finding was the need for an intermediary service. They wanted somebody they could contact in an everyday setting, to reach out to without it feeling like a major decision. This was more than a request from the public; it was a desperate plea. People experiencing domestic abuse wanted a drop-in service in a neutral environment with a trusted professional who could listen to them and signpost to the most appropriate service. People did not want to be alone when contacting the major services. They wanted an easily accessible intermediary. Both professionals and the public agreed that there was a considerable amount of suffering that was "sub-threshold" for the Police or Social Care but needed addressing. An intermediary service could support people in accessing charity and voluntary sector support. Participants also reported that a simple "Are you OK?" conversation in itself was enough to trigger change, which suggests that an intermediary service would be beneficial in its own right, as well as through referrals. This research was presented as oral presentations at two conferences and published as a report (with accompanying video resources that were created as part of the project) to Nottingham City Council, along with a dissemination event.39,40,41.

AL and JS conducted an NIHR-funded project which developed a co-produced educational intervention to support pharmacy staff in targeting pharmacy services towards under-served communities. This study highlighted the value of community pharmacy in addressing health inequalities. This study led to 6 research publications.

This project therefore proposes to co-develop and test the feasibility of an easily recognisable, accessible and discreet response service for people who are experiencing suicidal ideation or domestic abuse, available through community pharmacies. This will be done through the development of a complex health intervention followed by an evaluation of feasibility using the MRC framework for developing complex health interventions.

# STUDY OBJECTIVES AND PURPOSE

# PURPOSE

The primary aim is to co-develop and evaluate the feasibility of a community pharmacy response service / intervention for people in danger from domestic abuse or suicidal ideation.

# PRIMARY OBJECTIVE

How feasible and acceptable is a co-produced community pharmacy response intervention for identifying and referring people in danger from suicidal ideation or domestic abuse?

# SECONDARY OBJECTIVE(S)

The objectives of the study are:

- 1. To develop a point of contact and triage referral resource in partnership with relevant experts and local referral organisations, for both domestic abuse and suicidal ideation.
- 2. To co-develop (with lay survivors / people with insight and professionals) the scope and features of a discreet response intervention in community pharmacy, to include the name, logo, promotional strategy and protocol for delivery in a pharmacy.
- 3. To co-develop with patients / public and professionals a training package and mentoring support service for pharmacy staff delivering the intervention.
- 4. To deliver the intervention in a purposive sample of community pharmacies and collect feasibility data on intervention usage and consequent referrals.
- 5. To ascertain and evaluate client, public and professional views on accessibility, acceptability, implementation, feasibility and intervention fidelity in practice.
- 6. To evaluate the potential for the intervention to be scaled up for a future trial, including economic and statistical considerations.
- 7. To engage with the public and professionals to disseminate findings and reporting of the intervention as an output.

### **OUTCOME MEASURES/ENDPOINTS**

#### PRIMARY OUTCOME MEASURE/ENDPOINT

The primary outcome measure for this study will be the number of community pharmacy consultations for people enquiring about or seeking support for domestic violence or suicidal ideation, categorised per issue and level of severity.

#### SECONDARY ENDPOINTS/OUTCOMES

Secondary outcome measures are (i) subsequent management and referrals to support organisations (ii) client quality of life (based on EQ5D) (iii) acceptability of the service to clients (iv) client demographics (v) cost and economic considerations of the service.

#### **STUDY DESIGN**

- Phase 1: Intervention co-development involving one-to-one interviews, focus groups and coproduction workshops.
- Phase 2: Training of pharmacy staff followed by a Feasibility Cluster Randomised Control Trial (in community pharmacies) and evaluation (qualitative focus groups, customer interviews, e-survey and summary workshop).

#### DATA ANALYSIS

All data analysis will be undertaken by the research team at the University of Lincoln.

#### Qualitative data

Qualitative data will be generated in the interviews, focus groups and workshops. Following transcription, data will be analysed using framework analysis. This will involve an initial iterative process of open coding and according to a coding framework. After the coding process has been completed, a more refined and selective process of 'coding on' will be undertaken to differentiate, contrast and narrate the emerging themes that are of relevance to meeting the study's objectives. The qualitative software programme NVIVO 11 will be used to organise the data.

#### Quantitative data

There are three sets of quantitative data: the evaluation of pharmacy staff learning, the intervention measures and the community e-survey. To assess the impact on pharmacy staff learning (using the CPD Reaction Questionnaire), baseline and post-training data scores will be compared. For both the CPD Reaction Questionnaire and the community e-survey, categorical variables will be analysed using the chi-squared test or Fisher's exact test as appropriate. Continuous data will be analysed using the within-group t-test or Wilcoxon signed rank-test as appropriate. Statistical significance will be assessed at the 5% (two-sided) level. All statistical analyses will be conducted using IBM Statistical Package for Social Sciences (SPSS) 22.

All client and pharmacy intervention / control data will be processed using R Version 3. The demographics and characteristics of the samples will be initially summarised using frequencies and percentages for categorical variables and mean and standard deviation (if normally distributed) or median and interquartile range (if not normally distributed) for continuous variables.

The main outcome in this feasibility study is the number of community pharmacy consultations for people enquiring about or seeking support for domestic violence or suicidal ideation per issue and level of severity. Descriptive comparisons will be made between intervention and control pharmacies. Appropriate multivariable linear regression models will explore differences between intervention and control groups in means and 95% CIs. As the feasibility study is not powered to detect effectiveness, the focus will be on whether 95 % CIs include a meaningful difference. This will seek to inform a sample size calculation for a future definitive trial.

The final evaluation of feasibility will involve the integration of the qualitative and quantitative data and will include an economic evaluation. In the economic analysis, a societal perspective will be taken into consideration. Business data including staff time will be used to inform the findings. Cost per client will be estimated by dividing the costs of the response service by the total number of clients accessing the service in the intervention group. An incremental cost-effectiveness ratio (ICER) will be determined to explore the affordability and potential cost-effectiveness of the intervention and inform a future trail rather than provide a definitive comparison

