### Phase 2: Feasibility Randomised Control Trial

**D. Recruitment and Training –** 12 community pharmacies will be recruited to take part in the study, with 8 as interventions and 4 as controls. Purposive sampling will be used to recruit three pharmacies per category of rural/small pharmacy, rural/commercial store, uon-rural/small pharmacy, non-rural/commercial store, with a spread across different socio-economic areas (based on deprivation index from Office for National Statistics). Randomisation will then be conducted to give 2 pharmacies from each of the four categories as interventions (total of 8), and 1 pharmacy from each of the four categories as a control (total of 4).

A minimum of three members of staff from each pharmacy will be recruited in the intervention pharmacies, with one of them being a pharmacist (total of 24 staff). Recruitment will be through the Local Pharmaceutical Committee (LPC) and will involve consent from the pharmacy employer for chain pharmacies. The LPC are partners in this study and as such are very supportive and do not foresee any problems with recruiting pharmacies. Information sheets and consent forms will be provided, both for consent of the pharmacy to take part, and for staff participants. Intervention pharmacies will receive an expenses payment of £1500, and control pharmacies a payment of £500.

The participating staff will then be trained in two evening sessions, which will be interactive and involve active learning. The pharmacy sites will be visited to ensure they meet the requirements for the study, which are to have regular staff and pharmacist (not locums), and to have a consultation room that is sound-proof. Participants will be asked to complete the Continuing Professional Development (CPD) Reaction Questionnaire before and after the training. This is a validated tool for assessing the impact of CPD activities on health professionals' behaviour intentions in clinical practice. This will allow us to assess their perceived level of knowledge, skills and attitudes for delivering the intervention. Each participating member of staff will also undertake 2 mock consultations with a member of the research team to embed their learning in situ. One consultation will be on suicide prevention and one on domestic abuse.

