#### 3. Public e-survey

The themes from the combined qualitative analysis will be used to form the basis of a quantitative e-survey. The rationale of the community survey is to measure the wider awareness of the service.

The e-survey will be distributed through local community networks (the same as were used in the promotional strategy), and the intervention pharmacies, and will evaluate public awareness and attitudes towards acceptability and accessibility. The survey will contain a participant information section. A total of 600 responses will be aimed for. Assuming a response rate of 50%, 1200 people will need to be specifically targeted. Students will be employed through the University of Lincoln's "Campus Jobs" scheme to conduct market research by approaching passers-by in community settings and promoting on social media. Data from the survey will be analysed using descriptive and comparative statistics for different demographic groups.

**G. Feasibility of the intervention -** A summary workshop will be held with the 24 staff members, plus PPIE panel and Study Management Group will be held to explore the feasibility of the intervention as a possible

service and to review and finalise the intervention. Consideration will be given to: any unintended or adverse consequences, the degree of local adaptation that would be required, who would deliver the training, who would deliver the mentoring, factors that facilitate/hinder the intervention, and its overall benefits and limitations of the intervention. This would enable us to fully describe the intervention, and its components, plus the extent to which it can be adapted, so that it can be reproduced faithfully. The topic guide for the workshop will be based on the Consolidated Framework for Implementation Research. Pharmacy staff participants will receive a £75 for participating as a token of appreciation (or a voucher if preferred), as this will be an additional event after the 6 months implementation, for which the pharmacy received a fee.

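### One shared test list gives categorical CPD questionnaire items an unpaired test and, read naturally, gives continuous e-survey items a paired one (minor)

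*Protocol*

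**What the plan says.** The Quantitative data section of the Protocol treats the two instruments together: "For both the CPD Reaction Questionnaire and the community e-survey, categorical variables will be analysed using the chi-squared test", with Fisher's exact test as the alternative where appropriate. The next sentence reads "Continuous data will be analysed using the within-group t-test or Wilcoxon signed rank-test as appropriate". It names no data set and excepts none. The level is fixed for both: "Statistical significance will be assessed at the 5% (two-sided) level".

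The designs are described elsewhere. For the CPD questionnaire, section D (Recruitment and Training) says "Participants will be asked to complete the Continuing Professional Development (CPD) Reaction Questionnaire before and after the training", with a "total of 24 staff". The stated purpose is that "baseline and post-training data scores will be compared".

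For the e-survey, section F.3 (Public e-survey) builds the questionnaire from themes found in the earlier qualitative work, describes one round of about 600 responses, and says "Data from the survey will be analysed using descriptive and comparative statistics for different demographic groups". The Size of sample section plans it around a yes/no item on awareness of the service.

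**The concern.** Chi-squared and Fisher's test assume independent observations. In a before-after comparison of 24 people they count 48 separate answers and discard who changed, which is the information a before-after design collects. A within-group t-test or signed-rank test needs two measurements on the same unit. The e-survey gives one per respondent, and its planned comparisons are between different people.

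The as-appropriate qualifiers do not cure this. The first chooses between chi-squared and Fisher, the second between the t-test and Wilcoxon. Neither moves between paired and unpaired methods. This is therefore a stated rule that does not fit, not a detail left to a later analysis plan.

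At stake are the inference on any categorical CPD item, and whether the stated test can be carried out on any continuous or scale item in the e-survey.

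**Working it through.** **Step 1: match test to structure.**

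| Data set and variable type | Structure | Test in the Protocol | Fits? |
|---|---|---|---|
| CPD scores | paired, same staff | within-group t / signed-rank | yes |
| CPD categorical items | paired, same staff | chi-squared / Fisher | no |
| E-survey categorical items (awareness) | independent groups | chi-squared / Fisher | yes |
| E-survey continuous or scale items | independent groups, one wave | within-group t / signed-rank (natural reading) | no |

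Two of the four cells are mismatched, one in each data set.

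**Step 2: what ignoring the pairing does.** The Protocol gives no power or size figure for these tests, so there is none to reproduce. Its staff count does reproduce: 8 pharmacies × 3 = 24. Everything else here is an assumption: proportions of 40% and 70%, and a within-person correlation φ from 0 to 0.5.

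A worked table first. Take 10/24 yes before and 16/24 after. Chi-squared gives p = 0.082 and Fisher p = 0.147, however the pairs line up. Exact McNemar gives p = 0.031 if all 6 changes are from no to yes (2 × 0.5⁶). It gives p = 0.238 if 12 staff change one way and 6 the other. The prescribed tests cannot tell these cases apart.

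**Step 3: direction of the error.** With no change from p = 0.4, the unpaired variance of the difference is 2 × 0.4 × 0.6 / 24 = 0.020. The true variance is 0.020 × (1 − φ), which is 0.010 at φ = 0.5. The standard error is overstated by √2 = 1.41, so positive correlation makes the test conservative.

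**Step 4: size and power.** The joint probabilities are p₁₁ = p₀p₁ + φ√(p₀q₀p₁q₁), p₁₀ = p₀ − p₁₁, p₀₁ = p₁ − p₁₁, with q = 1 − p. For 40% to 70% at φ = 0.5, p₁₁ = 0.28 + 0.5 × √(0.24 × 0.21) = 0.392. Summing the multinomial probabilities over every possible table of 24 pairs at two-sided 5% gives:

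| φ | Scenario | Chi-squared | Fisher | Exact McNemar | Asymptotic McNemar |
|---|---|---|---|---|---|
| 0.5 | no change, 40% | 0.75% | 0.22% | 1.19% | 4.9% |
| 0.5 | 40% to 70% | 0.61 | 0.44 | 0.73 | 0.90 |
| 0.3 | 40% to 70% | 0.60 | 0.46 | 0.57 | 0.68 |
| 0 | 40% to 70% | 0.59 | 0.47 | 0.42 | 0.52 |

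The average proportion in the 40% to 70% case is 0.55, so the expected counts are 24 × 0.55 = 13.2 and 24 × 0.45 = 10.8. By the usual expected-count rule chi-squared would be the test used, so it is the fairer comparator.

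**Step 5: the e-survey.** No arithmetic is needed. With one response per person there is no within-person difference, so neither paired test can be computed for a contrast between demographic groups.

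**The case against.** The strongest reply is that the main comparison in each data set is handled correctly. Training impact is framed as a comparison of scores, which get a paired test. The survey's rationale is awareness, a yes/no item, which gets chi-squared or Fisher. That stands. A reader might infer that both data sets get the wrong test throughout, or that the p-values and intervals for training impact are wrong. The documents do not support either reading, and the Quantitative data section states no interval for the CPD data.

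It can also be said that both mismatched cells rest on inference. No categorical CPD item is singled out for a before-after comparison, no continuous e-survey variable is named, and the sentence on continuous data could have been meant for the CPD scores alone. This stands in part. The CPD half needs little inference, because the wording assigns chi-squared or Fisher to that questionnaire by name. The e-survey half does depend on reading the sentence as continuing from the one before it. That is the natural reading, but it is not stated.

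The size can be overstated too. Setting Fisher against exact McNemar at φ = 0.5 (0.44 against 0.73) suggests a large loss. Against chi-squared the gap is 0.12 (0.61 against 0.73), and at φ = 0.3 it reverses (0.60 against 0.57). Exact McNemar is itself conservative, so not all of the shortfall in size comes from ignoring the pairing.

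Finally, no progression decision uses these p-values. In Appendix 1, criterion 9 turns on completion and the share of staff feeling adequately trained, criterion 28 on the number of responses, and criterion 33 on the percentage aware. That stands and limits the severity.

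**Conclusion.** The point holds in a narrow form and is minor. One test list serves a paired and an unpaired data set, so categorical CPD items are assigned tests that ignore the pairing and, on the natural reading, continuous e-survey items are assigned tests that cannot be computed.

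For the CPD items the error is conservative when a person's answers are positively correlated, so it does not create false claims that training worked. The loss depends on assumptions that the Protocol does not supply. It is visible at a correlation of 0.5. At 0.3 or below, chi-squared is no less powerful than exact McNemar. A higher severity would require the primary outcome, a listed secondary outcome or a progression criterion to depend on these tests, and none does.

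**What to change.** Replace the shared list in the Quantitative data section with one line per data set.

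- CPD Reaction Questionnaire: paired t-test or Wilcoxon signed-rank for scores; McNemar for two-category items, or a marginal homogeneity test for more than two. Pre- and post-training forms are linked by the study identity number already assigned under Data Protection and Patient Confidentiality.
- E-survey: chi-squared or Fisher for categorical items; for any continuous or scale item compared between demographic groups, independent-samples t-test or ANOVA, or Mann-Whitney or Kruskal-Wallis.

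The cost is two sentences. No new data are needed, provided the linking number is on both CPD forms when they are completed.

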# STUDY SETTING

- One-to-one interviews will take place in a setting that is most convenient to the participant.
- Focus groups and all workshops will take place at the School of Pharmacy, University of Lincoln.
- The feasibility study will involve community pharmacies recruited from the Lincolnshire area.

# **SELECTION OF PARTICIPANTS**

# ELIGIBILITY CRITERIA

# Inclusion Criteria Phase 1: Co-development of the complex intervention

Stakeholders (for interviews)

(a) Aged  $\geq$ 18 years

(b) Representative of an organisation(s) that offer domestic abuse / suicide prevention or related services (for example, drug & alcohol services)

Lay people (for focus groups)

(a) Aged ≥18 years

(b) Survivor of domestic violence, suicidal ideation beliefs or interest/experience in supporting others in these circumstances

(c) Person with insight into and interest in supporting others for domestic abuse / suicidal ideation

Pharmacy staff (for workshops)

- (a) Aged  $\geq$ 18 years
- (b) Current or recently worked for a community pharmacy organisation

# Phase 2: Feasibility cluster Randomised Control Trial

Pharmacy staff (to be trained, deliver the intervention, and participate in focus group and feasibility workshop)

- (a) Aged ≥18 years
- (b) Employed by a community pharmacy that is in the study

Clients (service users, (recipients of the intervention)

- (a) Aged  $\geq$ 18 years
- (b) Asking about or requiring support about domestic abuse / suicidal ideation

Pharmacy customers (for interviews)

(a) Aged  $\geq$ 18 years

(b) Familiar with the intervention pharmacy

General public (for community e-survey)

(a) Aged  $\geq$ 18 years

(b) Resident in Lincolnshire

# **Exclusion Criteria**

# Phase 1: Co-development of the complex intervention

Stakeholders

(a) Those without specialist knowledge of delivering services to people experiencing domestic abuse / suicidal ideation and related issues

Lay people (for focus groups)

- (a) Unable or unwilling to give consent
- (b) People in an acute state of distress

Pharmacy staff (for workshops)

(a) Pharmacy staff who are in non-customer facing roles

# Phase 2: Feasibility cluster Randomised Control Trial

Pharmacy staff

- (a) All staff in pharmacies where consent is absent from the Pharmacy's Head office / Pharmacy Owner
- (b) Pharmacy staff in pharmacies that are not in the study
- (c) Locum pharmacy staff (not on a regular employed contract with the pharmacy
- (d) Pharmacy staff in a non-customer facing role

Clients (service users)

- (a) Aged under 18 years
- (b) Any participant unwilling or unable (i.e. lacking capacity) to provide consent

Pharmacy customers

- (a) Aged under 18 years
- (b) People who have accessed the response service
- (c) Any participant unwilling or unable (i.e. lacking capacity) to provide consent

# General public

- (a) Aged under 18 years
- (b) Not resident in Lincolnshire

# Sampling Phase 1:

Stakeholder interviews = 8 participants

2 x Lay focus groups (8 participants in each focus group) = 16 participants

3 x Co-development workshops (8 lay people and 4 pharmacy staff representatives in each workshop) = 36 participants

# Phase 2:

# A minimum of 3 x Staff per intervention pharmacy (after sampling of the pharmacies and randomisation to intervention/control = 24 participants

3 x Focus groups with pharmacy staff members (who delivered the intervention) = 24 participants (as above)

Customer interviews (up to three from each pharmacy) = 24 participants

E-survey = 600 participant responses

Summary workshop (24 staff members - NB already countered above, plus PPIE panel (~8) and Study Management Group (~6) = 46 participants

